6.3 PATIENT SETS ANALYSED

The following nested patient sets are defined:

- Randomised set (RS):

This patient set includes all patients who signed informed consent form and were also randomised, regardless whether the patient was treated with study medication or not.

- Treated set (TS):

This patient set is nested within RS and includes all patients who were dispensed study medication and were documented to have taken any dose of study medication. TS will be used for patient disposition, demographics and baseline disease characteristics, concomitant therapies, treatment compliance, treatment exposure and safety analyses (including AEs and vital signs).

- Full analysis set (FAS):

This patient set is nested within TS and includes patients who had baseline measurement and at least one post-baseline measurement for the primary endpoint or a secondary endpoint. The FAS will be used for the efficacy analyses. Assignment to the FAS will be done after implementation of any data handling rules which set measurements to missing.

- Per protocol set (PPS):

This patient set is nested within FAS and includes only patients who had no important PVs which are specified to be excluded from the PPS (Table 6.3: 1). The PPS will be used for sensitivity analysis if PPS less than 90% of FAS.

The final decision regarding which patients are excluded from PPS will be made at BRPM prior to data unblinding.

Table 6.3: 1 Patient sets analysed

Class of endpoint	Patient Sets		
	TS	FAS	PPS
Primary endpoint		primary analysis	supportive analysis*
Secondary endpoints		X	
Further endpoints		X	
Safety endpoints	X		
Demographic/baseline endpoints/exposure	X		

* Adding only when the number of patients in PPS is less than 90% of the number of patients in FAS as sensitivity analysis.

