7.3.1 Primary endpoint analyses

Primary analysis will be performed in all patients who signed informed consent, are randomised (RS) and are documented to have taken any dose of study medication (TS), and have non-missing baseline at Visit 2 and non-missing post-dose baseline measurements of IC at rest for primary endpoint. This set is called Full Analysis set (FAS) and assignment to the FAS will be done after implementation of any data handling rules which set measurements to missing.

The primary analysis will be conducted using MMRM including treatment and period as categorical fixed effects, study baseline as a covariate and patient as a random effect treatment. Compound symmetry will be used as a covariance structure for within patient variation. The SAS procedure MIXED will be used involving the restricted maximum likelihood estimation and the Kenward-Roger approximation for denominator degrees of freedom. This approach is described in [\[R10-4391\]](#). Adjusted mean values as well as

treatment contrasts will be presented together with the 95% confidence intervals (CI) and p-values.

After blinded review of the magnitude and potential impact of any serious protocol violations, a subset of the data corresponding to those patients without serious deviations from the protocol will be created. This will be called the Per-Protocol Set (PPS). If the number of patients in PPS is less than 90% of the number of patients in FAS, the primary analyses will also be performed on PPS. These will be supportive analyses to assess the robustness of the primary analysis using FAS.

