Table 6.2: 1 (cont'd) Important protocol violations

Category/ Code	Description	Example/Comment	Excluded from	Automatic/ Manual
Z	Other			
Z1	Serious GCP non-compliance	Manual PVs reported by CML/CRA which are considered as important. Carefully reviewed, described and documented in DBL meeting minutes.	PPS	Manual
Z2	Other PV affecting efficacy and possibly safety	Additional PV identified through monitoring which impacts the primary analysis and possibly patient's rights or safety. Carefully reviewed and documented in BRPM minutes and comment field of IPV ADS.	PPS	Manual
Z3	Other PV affecting safety only	Additional PV identified through monitoring which impacts patient's rights or safety. Carefully reviewed and documented in BRPM minutes and comment field of IPV ADS.	None	Manual
Z4	Missing value of all primary and secondary endpoints	Patients who had baseline measurement and at least one post-baseline measurement for the primary endpoint or a secondary endpoint will be included FAS. Patient who does not have above measurement is IPV.	FAS	Automatic

CML = Local Clinical Monitor

CRA = Clinical Research Associate

Note: Missing visits, evaluations, and tests are considered as missing data, but not protocol deviations.

DBL = Data Base Lock

ADS = Analysis Data Set

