6.6 HANDLING OF MISSING DATA AND OUTLIERS

Completely missing visits not due to worsening of study disease will not be imputed and will stay as missing, because such missing data are considered as randomly missing data and will be handled in the mixed model repeated measures model.

Completely missing visits/weeks due to the patient discontinuing due to worsening of study disease will be imputed with the baseline value.

It could happen that a patient needed therapy for COPD symptoms at a clinic visit. This therapy was entered on the rescue medication of electronic Case Report Form (eCRF). This may or may not be the rescue medication provided by Boehringer Ingelheim (BI). For purposes of the imputation rules this will be termed “rescue medication” regardless of whether or not it was BI-supplied rescue medication.

For spirometry data, the records which are flagged as “unacceptable” by the vendor (ERT) will be administratively set to missing and treated as randomly missing data for imputation purpose.

The following rules are used for exercise data:

- [REDACTED]
- Measurements of oxygen saturation, blood pressure and heart rate which are missing during recovery will not be imputed.
- [REDACTED]

The following rules will be used for spirometry data which were collected at Visits 2, 3 and 4:

- Since there is only one spirometry measurement at each on-treatment clinic visit, rescue medication use on or before the spirometry measurement or rescue use with unknown time will both result in all spirometry measurements for the visit being set to missing. In these cases the entire visit will be imputed with baseline.
- If spirometry measurements for an entire visit are completely missing because a patient discontinued due to worsening of study disease, then all data for this visit will be imputed with baseline.
- Randomly missing spirometry measurements will not be imputed.

Missing safety data will not be imputed with the exception of missing or incomplete AE dates which will be imputed according to BI guideline 'Handling of missing and incomplete AE dates' (1).

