6.7 BASELINE, TIME WINDOWS AND CALCULATED VISITS

Measurements collected at Visit 2 will be used as baseline with the exception of the activity endpoints which are averaged over 2 weeks. For endpoints of physical activity monitoring, baseline will be the average value in two weeks prior the day before first administration (Visit 2) except for Day -2 and Day -1. These will be defined as "Study baseline" which will be common baseline for both period 1 and period 2.

Planned and actual study day will be included in the analysis data sets. These will both be calculated relative to the beginning of the study and to the beginning of respective study periods in the crossover design as indicated in the following table.

Table 6.7: 1 Planned and actual study days, and time windows

Visit	Relative to period start		Relative to study start	
	Planned day	Actual day	Planned day	Actual day
2	1	1	1	1
3	43	Visit 3 date – Visit 2 date + 1	43	Visit 3 date – Visit 2 date + 1
4	43	Visit 4 date – Visit 3 date + 1	85	Visit 4 date – Visit 2 date + 1
5	3	Visit 5 date – Visit 4 date + 1	106	Visit 5 date – Visit 2 date + 1

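### Does the SAP's wider full analysis set distort the primary IC analysis by admitting patients with no measured on-treatment IC?

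*SAP*

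**What the plan says.** Protocol 7.3.1 builds the set for the primary analysis from randomised, treated patients who "have non-missing baseline at Visit 2 and non-missing post-dose baseline measurements of IC at rest for primary endpoint". The phrase is garbled and does not say whether one or both periods are needed.

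SAP 6.3 defines one FAS for all efficacy endpoints. It "includes patients who had baseline measurement and at least one post-baseline measurement for the primary endpoint or a secondary endpoint". Code Z4 in SAP Table 6.2: 1 repeats the rule: "Patients who had baseline measurement and at least one post-baseline measurement for the primary endpoint or a secondary endpoint will be included FAS". SAP Table 6.3: 1 uses this set for the primary analysis.

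On order, SAP 6.3 says: "Assignment to the FAS will be done after implementation of any data handling rules which set measurements to missing". Protocol 7.3.1 says the same. Neither places the step before or after imputation.

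SAP 6.6 has two rules that put baseline in place of a lost IC:
- After stopping for worsening: "Completely missing visits/weeks due to the patient discontinuing due to worsening of study disease will be imputed with the baseline value".
- For rescue use at or before the measurement, or at an unrecorded time: "rescue use with unknown time will both result in all spirometry measurements for the visit being set to missing", and then "In these cases the entire visit will be imputed with baseline".

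Spirometry missing at random is not imputed. Under SAP 6.7 baseline is a single value per patient, "which will be common baseline for both period 1 and period 2".

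**The concern.** The two documents can give different patient lists for the same analysis. Suppose the FAS is fixed after values are set to missing but before they are imputed. A patient who lost IC at both visits through rescue use or worsening, but has an activity or walk value, is then outside the protocol's set and inside the SAP's. Imputation gives that patient the same IC in both periods, so the treatment difference is exactly zero although no on-treatment IC was measured.

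Such zeros would pull the estimate towards no effect and make its confidence interval slightly too narrow. The FAS count is also the denominator of the 90% rule that decides whether the supportive per-protocol (PPS) analysis is run. An unclear primary analysis set is also an easy target for criticism after unblinding.

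**Working it through.** **Planned figure.** Protocol 7.7 gives a difference of 0.1 L, SD 0.41 L, two-sided alpha 0.05, 90% power, 180 patients and a one-sample t-test. The exact noncentral t calculation gives 179 patients, and power at 180 is 90.2%. For SD 0.40 L it gives 171, as stated. The plan's figures are reproduced, so 0.41 L can be used as the SD of the within-patient difference.

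**Who can be affected.** The model code in SAP section 9 uses only records with IC and baseline present. A patient whose IC is missing at random therefore adds nothing to the estimate, whichever FAS applies. Only patients imputed at both visits matter. The routes are:
- rescue use at both Visit 3 and Visit 4, although Protocol 4.2.1.1 and 6.1 have such visits rescheduled;
- stopping for worsening late in period 1 with some activity data, although Protocol 5.2.3 has the monitor worn only in the two weeks before a visit, and the walk test is not among the withdrawal procedures in 6.2.3;
- rescue use at Visit 3, then stopping for worsening in period 2.

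Their number, k, is not in the documents. I assume k = 1 to 5 of 180.

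**Effect on the estimate.** Let w = (180 − k)/180. With k differences set to zero:
- estimate = 0.1 × w
- variance = w × 0.41² + w(1 − w) × 0.1²
- SE, SAP set = √(variance/180)
- SE, protocol set = 0.41/√(180 − k), with the estimate staying at 0.1 L

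For k = 2, w = 0.98889. Variance = 0.98889 × 0.1681 + 0.98889 × 0.01111 × 0.01 = 0.16634, so SE = √(0.16634/180) = 0.0304. The protocol set gives 0.41/√178 = 0.0307.

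| k | Estimate, SAP set (L) | SE, SAP set | SE, protocol set | SE ratio | Power, SAP set | Power, protocol set |
|---|---|---|---|---|---|---|
| 1 | 0.0994 | 0.0305 | 0.0306 | 0.995 | 90.1% | 90.1% |
| 2 | 0.0989 | 0.0304 | 0.0307 | 0.989 | 89.9% | 89.9% |
| 5 | 0.0972 | 0.0302 | 0.0310 | 0.973 | 89.4% | 89.4% |

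Estimate and SE shrink almost together. At k = 5 the ratio of estimate to SE is 0.09722/0.03016 = 3.22 for the SAP set and 0.1/0.03099 = 3.23 for the protocol set.

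**Simulation.** In 20,000 period-adjusted crossover trials per scenario, with affected patients spread evenly over the sequences and k up to 10, type I error was 5.0 to 5.3% under both sets. Power differed by less than 0.1 percentage point.

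**PPS rule.** Let j be all patients in the SAP set but not the protocol set, including those with IC missing at random. Take an SAP FAS of 180.
- If all j stay in the PPS, the decision differs only at a PPS of 162. There 162/180 = 0.900 does not trigger the analysis, whereas 161/179 = 0.8994 (j = 1) and 157/175 = 0.8971 (j = 5) do.
- If all j leave the PPS for another reason, nothing differs at j = 1. At j = 2 it differs only at 161 (161/180 = 0.894 against 161/178 = 0.904). At j = 5 it differs at 158 to 161 (158/180 = 0.878 against 158/175 = 0.903).

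In each case the only thing at stake is whether a supportive analysis is run.

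**The case for a change.** The strongest case for a change is that the mismatch is in the text. Z4 is marked as an automatic check, so the wider rule is the one that would be programmed. An unstated order of steps decides who is in the primary analysis. Patients with IC missing at random separate the two sets whatever that order is. One sentence before unblinding would settle it.

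The wording difference and the silence on order both stand. The consequence does not:
- SAP 6.6 sets rescue-affected values to missing and imputes them within one rule. Counting the imputed IC as available is a fair reading. The imputed patients are then in both sets, and the zeros no longer depend on which set is used.
- The zeros come from the imputation rule, not from the FAS. Narrowing the FAS leaves the same rule in force for a patient with one measured and one imputed visit.
- Patients with IC missing at random affect a count, not the estimate.

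The size also depends on reading the protocol as needing one measured on-treatment IC. If both periods were required, anyone with a single IC would also fall outside the protocol set, and k and j could exceed 5. That reading fits poorly with Protocol 7.5, which leaves completely missing visits to the mixed model. A set restricted to complete pairs would leave the model no missing visits to handle.

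**Conclusion.** No change to the plan follows. Protocol 7.3.1 and SAP 6.3 do word the FAS differently, but following the SAP as written still gives a sound primary conclusion. With k = 1 to 5 of 180 the estimate moves from 0.1 L to between 0.0994 and 0.0972 L and the interval narrows by 0.5 to 2.7%. Power is the same to within 0.1 percentage point, and type I error stays near 5%. The small shift is towards no difference, so it does not favour the combination.

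The choice of set is a fair trade-off. The wider FAS keeps patients who worsened or needed rescue and scores them as no gain over baseline. The narrower set would exclude them for reasons linked to outcome. Either can be defended. The order of assignment and imputation is a detail that the analysts can settle and document at the blinded review meeting that the SAP already plans. The protocol leaves analysis details to the SAP, and blacked-out section 4 may already declare the different FAS, so an undeclared conflict cannot be shown.

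This rests on the assumed k, on the planned 0.1 L and 0.41 L, on affected patients being spread roughly evenly over the two sequences, and on one measured on-treatment IC being enough for the protocol's set.

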6.4 SUBGROUPS

No subgroups are defined and no subgroup analyses are planned.

6.5 POOLING OF CENTRES

This section is not applicable because centre/country is not included in the statistical model.

6.6 HANDLING OF MISSING DATA AND OUTLIERS

Completely missing visits not due to worsening of study disease will not be imputed and will stay as missing, because such missing data are considered as randomly missing data and will be handled in the mixed model repeated measures model.

Completely missing visits/weeks due to the patient discontinuing due to worsening of study disease will be imputed with the baseline value.

It could happen that a patient needed therapy for COPD symptoms at a clinic visit. This therapy was entered on the rescue medication of electronic Case Report Form (eCRF). This may or may not be the rescue medication provided by Boehringer Ingelheim (BI). For purposes of the imputation rules this will be termed “rescue medication” regardless of whether or not it was BI-supplied rescue medication.

For spirometry data, the records which are flagged as “unacceptable” by the vendor (ERT) will be administratively set to missing and treated as randomly missing data for imputation purpose.

The following rules are used for exercise data:

- [REDACTED]
- Measurements of oxygen saturation, blood pressure and heart rate which are missing during recovery will not be imputed.
- [REDACTED]

The following rules will be used for spirometry data which were collected at Visits 2, 3 and 4:

- Since there is only one spirometry measurement at each on-treatment clinic visit, rescue medication use on or before the spirometry measurement or rescue use with unknown time will both result in all spirometry measurements for the visit being set to missing. In these cases the entire visit will be imputed with baseline.
- If spirometry measurements for an entire visit are completely missing because a patient discontinued due to worsening of study disease, then all data for this visit will be imputed with baseline.
- Randomly missing spirometry measurements will not be imputed.

Missing safety data will not be imputed with the exception of missing or incomplete AE dates which will be imputed according to BI guideline 'Handling of missing and incomplete AE dates' (1).

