- ⁴ A preliminary check of in-/exclusion criteria is recommended at Visit 0 to avoid unnecessary washout procedures in non-eligible patients.
- ⁵ To be performed only if relevant findings at Visit 4/EOT.
- ⁶ Women of child-bearing potential: pregnancy test at Visit 1 and Visit 4/EOT
- ⁷ The patient will be instructed in the use of the RESPIMAT, but patient **should not** inhale from the training inhaler at Visit 2.
- ⁸ Rescue medication as salbutamol is prescribed at visit 0. Rescue medication will be collected and prescribed on subsequent visits by investigators as needed. All rescue medication for the trial to be confirmed to be collected at Visit 4/EOT.
- ⁹ Pre- and post-bronchodilator (400 µg salbutamol) [note: reversibility is not an inclusion criterion], Spirometry measurement; FVC and FEV₁ only.
- ¹⁰ Baseline spirometry measurement FEV₁, FVC, SVC, and IC.
- ¹¹ Morning post-dose spirometry

Proprietary confidential information © 2015 Boehringer Ingelheim International GmbH or one or more of its affiliated companies

- FEV₁ and FVC: 30 min post-morning dose as starting time
- IC and SVC measurement: 60 min post-morning dose as starting time

12
13

Prior to the start of PFTs are performed.

[REDACTED]

14

Patients should wear and measure activity monitor (3-axis accelerator) every day for 2 weeks prior to Visit 2, Visit 3 and Visit 4/EOT.

15

[REDACTED]

16

17

Site staff will telephone the patients 15 days and 8 days prior to the next planned Visit and remind them to wear physical activity monitor every day. An assessment of adverse events and of concomitant therapy should be performed from the last assessment.

18

Trial medication dispensed at Visit 2 should be administrated at clinic at Visit 3 and trial medication dispensed at Visit 3 should be administrated at clinic at Visit 4/EOT. Newly assigned trial medication at Visit 3 should be administered next day of Visit 3.

19

[REDACTED]

20

Refer to [Appendix 10.8. mMRC](#)

21

Training of 6MWT

22

Refer to [Appendix 10.11](#)

23

Training of patient diary at Visit 1. Dispense of the diary at Visit 1, Visit 2 and Visit 3. Reviewing and collection of the diary at Visit 2, Visit 3 and Visit 4/EOT.

TIMING OF PROCEDURES: VISIT1_SCREENING

	Start time					
	-	More than 30 min prior to Pre-dosing PFT	-10 to 0 min prior to administration salbutamol	administration salbutamol (0 min)	10 to 15 min after administration salbutamol	-
Medication washout compliance	X					
mMRC ¹	X					

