3.3.2 Inclusion criteria

1. All patients must sign an informed consent consistent with ICH-GCP guidelines prior to participation in the trial, which includes medication washout and restrictions.
2. All patients must have a diagnosis of chronic obstructive pulmonary disease ([P11-05865](#)) and must meet the following spirometric criteria:
Patients must have relatively stable airway obstruction with a post-bronchodilator FEV₁ < 80% of predicted normal (ECSC [[R94-1408](#)]); GOLD grade II-IV (P11-05865) and post-bronchodilator FEV₁/FVC < 70% at Visit 1 (see [Appendix 10.5](#) for ECSC predicted normal equations).
3. Male or female patients, aged ≥ 40 years.
4. Patients must be current or ex-smokers with a smoking history of more than 10 pack-years (see [Appendix 10.5](#) for calculations). Patients who have never smoked cigarettes must be excluded.
5. Patients with score on the modified Medical Research Council (mMRC) ≥ 1.
6. Patients who walk < 400 meters of 6MWT and have a score on the modified Borg ≥ 4 at the end of 6MWT at Visit 2.
7. Patients must be able to perform technically acceptable pulmonary function tests (spirometry), to use the physical activity monitor and must be able to complete 6MWT during the study period as required in the protocol.
8. Patients must be able to inhale medication in a competent manner from the RESPIMAT Inhaler ([Appendix 10.1](#)) and from a metered dose inhaler (MDI).

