7.7 DETERMINATION OF SAMPLE SIZE

For the primary endpoint of IC at rest after Week 6, results from the recent two BI studies (BI no.:1237.13[[c02094185](#)] and 1237.14[[c02094318](#)]) suggest that the standard deviation is approximately 0.4[L]. However, a little conservative 0.41[L] is deemed more appropriate due to uncertain prediction of drop-outs during tests for physical activities. In addition the IC at rest after Week 6 is estimated at 0.1 L for the difference between tiotropium + Olodaterol (LAMA/LABA FDC) and tiotropium (LAMA). To detect a difference of 0.1 L with the standard deviation of 0.41 L in the IC at rest between the two treatments with 90% power at the 2-sided alpha of 0.05, 180 patients will be required. Nquery Advisor nTerim ver.2.0 (MOT0-1, 1-sample t-test) was used for the sample size calculation.

Table 7.7: 1 Summary of sample size considerations

primary endpoint	Δ [L]	SD [L]	N (power)
IC at rest[L]	0.1	0.41	180 (90%)
		0.40	171 (90%)

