10.10 INSPIRATORY CAPACITY

In this trial inspiratory capacity measurements will be done at rest in combination with dosing of trial medication. A baseline measurement will be completed at Visit 2 prior to the exercise tests. IC measurements will also be performed 1.0 hours post morning dose on Visits 3 and 4 after measurement of FEV₁ and FVC. To supplement the information on IC manoeuvres in this chapter, a manual of procedures has been developed. More detailed information on IC measurements, calculations and post-test corrections etc. can be found in this manual which is filled in the ISF.

Resting IC

At each required visit, IC maneuvers will first be fully explained to the patient and then practiced at rest to confirm proper technique. Patients will be given a few breaths warning before an IC maneuver, a prompt for the maneuver (i.e., “At the end of the next normal breath out, take a deep breath all the way IN”), and then strong verbal encouragement to make a maximal effort before relaxing.

The patient will breathe through a mouthpiece attached to the spirometer. The patient should breathe quietly for a few breaths to achieve stable end expiratory lung volume (EELV) and then perform the inspiratory maneuver from EELV to TLC. The patient can be taken off the mouthpiece between maneuvers. The patient should return to stable EELV prior to performing the next maneuver. At least three reproducible IC measurements should be obtained (i.e., IC s.d. /IC mean values is 0.06 or less than 0.06) with a maximum of 5 measurements to be performed. The resting IC should be recorded as the mean of the two highest acceptable efforts.

Analysis / acceptability of IC maneuvers

If the effort appears sub-maximal or if anticipatory changes in breathing pattern occur immediately preceding a maneuver, then the IC should not be accepted unless it can be corrected post-test.

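### A treated patient whose whole Visit 2 IC is missing contributes nothing to the primary analysis, even with two valid on-treatment ICs, although the common baseline cancels from the treatment contrast

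*SAP*

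**What the plan says.** **When IC is measured.** Flow chart footnote 9 limits Visit 1 spirometry: "Spirometry measurement; FVC and FEV₁ only". Footnote 10 and Appendix 10.10 place the first IC at Visit 2, the randomisation visit, where it is also the baseline.

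**Checks at the site.** Inclusion criterion 7 reads "Patients must be able to perform technically acceptable pulmonary function tests (spirometry"), without naming IC. Eligibility is reviewed at Visit 2 (protocol 6.2.1). Appendix 10.10 has the manoeuvre practised at each required visit and adds: "At least three reproducible IC measurements should be obtained (i.e., IC s.d. /IC mean values is 0.06 or less than 0.06"), in no more than five efforts. It also rejects sub-maximal efforts that cannot be corrected.

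**What happens to a rejected value.** Under SAP 6.6, spirometry records that are flagged as unacceptable "by the vendor (ERT) will be administratively set to missing and treated as randomly missing data". The same section leaves randomly missing spirometry without imputation.

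**Who is analysed.** Protocol 7.3.1 restricts the FAS to patients who "have non-missing baseline at Visit 2 and non-missing post-dose baseline measurements of IC at rest for primary endpoint". SAP 6.3 is wider: a baseline and one post-baseline value for the primary or a secondary endpoint are enough. Both documents assign the FAS after values have been set to missing.

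**The model.** SAP section 9 fits treatment, period and the baseline of the endpoint (eptbase), with compound symmetry within patient. SAP 6.7 defines one study baseline common to both periods.

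**The concern.** In a two-period crossover the treatment effect is estimated mainly from the difference between each patient's two on-treatment values. A patient with valid ICs at Visits 3 and 4 therefore carries full information on the primary comparison, whatever happened to the Visit 2 measurement. The plan nevertheless makes that measurement a condition for using the pair. Because Visit 2 is the first occasion on which IC is recorded, some baselines may fail quality review in patients who later perform the manoeuvre well.

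At stake are randomised, treated patients lost from the primary analysis for a reason that does not affect the contrast. The two FAS definitions also disagree on whether such a patient belongs to the analysis set at all. Under the SAP definition the FAS could count a patient who contributes no data to the primary model.

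**Working it through.** **1. The path to exclusion.** Take a treated patient with valid ICs at Visits 3 and 4 whose Visit 2 IC is wholly rejected.
- Protocol 7.3.1: not in the FAS, because the Visit 2 IC is missing.
- SAP 6.3: may be in the FAS through a secondary endpoint such as walk distance. PROC MIXED then drops both records, because eptbase is missing.

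Both routes end with no contribution to the primary estimate.

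**2. What the baseline adds to the contrast.** Let B be the patient's study baseline with coefficient β, and let Y1 and Y2 be the period 1 and period 2 values. B enters both periods with the same value and the same β, so in Y2 − Y1 the term is βB − βB = 0. For complete pairs the treatment estimate does not depend on B.

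A simulated crossover confirms this. It used 180 patients, a true effect of 0.1 L and complete pairs, with these assumed values: between-patient SD 0.5 L, within-patient SD 0.29 L, baseline error SD 0.25 L.

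| Analysis | Patients | Estimate (L) | SE (L) |
|---|---|---|---|
| Baseline as covariate, complete | 180 | 0.1116 | 0.0291 |
| No baseline covariate | 180 | 0.1116 | 0.0291 |
| Baseline missing in 10%, set to mean | 180 | 0.1116 | 0.0291 |
| Baseline missing in 10%, patients dropped | 162 | 0.1154 | 0.0311 |

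A second simulated data set gave the same pattern: SE 0.0320 with complete data and with mean-filling, and 0.0342 with the patients dropped.

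**3. The plan's own sample size.** Protocol 7.7 takes an effect of 0.1 L, an SD of 0.41 L and a one-sample t-test, so 0.41 L acts as the SD of the within-patient difference. Its stated result is "with 90% power at the 2-sided alpha of 0.05, 180 patients will be required".
- Power = P(|T| > t(0.975, n − 1)), where T is noncentral t with n − 1 degrees of freedom and noncentrality (0.1/0.41)√n.
- The smallest n reaching 90% is 179 at SD 0.41 L (stated 180) and 171 at SD 0.40 L (stated 171). The plan's figures reproduce.
- At n = 180 and SD 0.41 L, the noncentrality is 0.2439 × 13.416 = 3.272 and power is 90.2%.

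**4. Power after the loss.** The rejection rate is not in the documents, so it is an assumption.

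| Assumed share of Visit 2 ICs wholly rejected | Pairs left of 180 | Power, SD 0.41 L | Power, SD 0.40 L |
|---|---|---|---|
| 0% | 180 | 90.2% | 91.6% |
| 2% | 176 | 89.6% | 91.0% |
| 5% | 171 | 88.7% | 90.2% |
| 10% | 162 | 87.0% | 88.6% |

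**5. The reserve.** Protocol 7.7 has no inflation for drop-out. It raises the SD from 0.40 to 0.41 L instead, which adds 180 − 171 = 9 patients, or 5% of 180. A 5% rejection rate would use all of that before any other loss.

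**The case against.** **Site checks already exist.** A reader might infer that nothing checks the baseline IC before randomisation. The documents do not support that. Criterion 7 covers spirometry, and the protocol treats IC as part of it: the flow chart row for pulmonary function testing, section 5.2.1 and section 5.7 all include IC. Protocol 6.2.1 lists the lung function tests at Visit 2 ahead of randomisation. Appendix 10.10 requires practice, repeatability and rejection of poor efforts, and SAP Table 6.2: 1 makes a breach of criterion 7 an important violation. What stands is narrower: no text names an acceptable Visit 2 IC as a condition of randomisation.

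**A stricter site rule would prevent the loss.** This too is tempting and unsupported. The exclusion follows from the vendor's flag, and nothing shows that an IC within the 0.06 limit would pass the vendor.

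**The mechanism depends on facts not given.** The rate, timing and criteria of vendor review are not stated. SAP 6.6 speaks of records. If a record is a single effort, the remaining efforts may still yield a baseline. The IC manual is held in the investigator site file and was not available. These points limit how often the problem arises, but they do not change what happens when it does.

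**Baseline does more than adjust.** SAP 6.6 also uses it to impute visits affected by rescue medication or by discontinuation for worsening disease. This is correct, and the fix must allow for it.

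**The effect is small.** If the SD is 0.40 L, as the source studies suggest, 171 pairs still give 90.2% power. This bears on priority. It does not justify discarding the pairs.

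**Conclusion.** The point holds as a modest and avoidable loss of precision. A missing Visit 2 IC removes a treated patient from the primary analysis under either FAS definition, and for complete pairs this gains nothing. Against 90.2% with all 180 pairs, the cost at SD 0.41 L is about 0.6, 1.5 or 3.2 percentage points of power at assumed rejection rates of 2%, 5% or 10%. The true rate may be lower or higher.

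A reader might go on to infer that the treatment estimate is biased. The documents give no ground for that: the rejected value is measured before any trial medication is taken, in a randomised crossover, so serious bias is not expected.

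The exact cancellation in the working applies to patients with both on-treatment ICs. For a patient with only one, the baseline does carry some information, and substituting a mean gives up that small part.

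**What to change.** 1. **Reconcile the FAS.** Give protocol 7.3.1 and SAP 6.3 one definition for the primary endpoint.
2. **Keep the pairs.** State in SAP 6.3 and 6.6, and in protocol 7.3.1, that any treated patient with an observed, usable on-treatment IC stays in the primary analysis. If the Visit 2 IC is missing, set the baseline covariate to the overall mean baseline.
3. **Limit the substitute to the covariate.** On-treatment visits that SAP 6.6 would impute with baseline stay missing for these patients. The present plan does not use those visits either, so nothing further is lost.
4. **Optional clarification.** Name IC in inclusion criterion 7, so that the Visit 2 eligibility review plainly covers the primary measurement.

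The cost is a few sentences, with no added test or visit. The statistical downside is a very small loss of covariate adjustment for the few patients affected. The change should be fixed before unblinding.
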